### **E.3. Aim 3: Conduct a Comprehensive Cost Study**

Building upon previous research, which reported that a glaucoma follow-up unit was cost effective compared to usual care, we will conduct a comprehensive cost study to estimate the intervention costs and cost-effectiveness of detecting eye diseases and vision impairment in a high-risk population. We have proposed an economic framework to minimize program costs, maximize program impact, and measure return on investment.

Building upon research by Holtzer-Goor KM, which reported that a glaucoma follow-up unit was cost effective compared to usual care, we will analyze the cost effectiveness of our enhanced intervention. The cost analysis will assess the feasibility of the study and identify areas where program costs can be minimized to estimate the net cost of replicating the intervention in additional communities to achieve similar outcomes once development and evaluation costs are removed.

E.3.a. Cost Measures for Aim 3: Cost measures will include intervention costs, glaucoma-related healthcare service use, glaucoma-related medications, and patient travel costs. The glaucoma exams of this project consist of five steps conducted by ophthalmic technicians, ophthalmologists, and study staff. The main tests performed on the patient include fundus photography, visual acuity, and a visual field analysis. Intervention costs will be measured for each step in the examination process and will include human costs as well as non-human costs. Trained research assistants and fellows will conduct site visits to observe and record the time each staff member takes to complete each step.

Direct personnel costs are calculated based on the mean duration for each step. Wage rates for personnel will be obtained based on job classifications, available from the 2013 US Bureau of Labor Statistics for Philadelphia. It

is assumed that most of the steps could be performed by ophthalmic technicians or medical assistants, whose wage rate is approximately \$16 per hour. Physicians participating in this project are estimated to have a wage rate of approximately \$87 per hour. Fringe benefits will be added to the wage costs at an estimated 35%. Time costs for each step are calculated with the following equation:

$$\text{Staff member} = \text{mean \# of minutes} \times (\text{wage rate} + \text{benefits})$$

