If additional staff members assisted with a step, then it will be assumed that they were there for half the time and additional time costs will be calculated as:

$$\text{Additional staff members} = (\text{mean \# of minutes}/2) \times (\text{wage rate for medical assistant} + \text{benefits})$$

Non-human costs to be collected include telemedicine platform, medical equipment and supplies, office supplies, community partners' recruitment, communication (internet hotspots), van rental and maintenance, and travel inclusive of fuel, and mileage. Medical equipment is expensive; however, it has been shown that once the investment is made, the operational costs are fairly low. Since the telemedicine platform and the medical equipment have been donated from WETD and the previous CDC-funded project, the cost of this study will be dramatically reduced.

The intervention will be examined to determine which services are billable to healthcare insurers, and the extent to which such reimbursement covers the costs. Even though it may not have a direct impact on exams, data on patient travel will also be collected. During check-out, project staff will ask patients about their satisfaction and type of transportation used. The costs of the transportation methods will be estimated based on the reported fares from Southeastern Pennsylvania Transportation Authority (SEPTA). Buses and subways cost \$2.25 per ride. Customized Community Transportation (CCT), for elderly and handicapped individuals, costs \$4 each way. When patients drive or take taxis, costs are estimated at \$1.65 and \$15 each way, respectively. Individuals who walk have no transportation costs. Previous studies have shown that "convenience of travel" contributed to patient satisfaction. Previous research has also reported that decreased patient traveling saved \$55 per visit. Additionally, work-productivity costs may be considered, since we are recruiting people who may be employed.

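### Aim 3 costs every additional staff member at an assumed half of the step and assistant pay, although the plan appears to record each person's time and to take wages by job; step costs can be misstated in either direction

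*Combined protocol and SAP*

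**What the plan says.** Section E.3.a describes an examination of five steps carried out by technicians, ophthalmologists and study staff. Research assistants and fellows visit the sites to "observe and record the time each staff member takes to complete each step". Wages are taken by job classification from 2013 labour statistics for Philadelphia: about $16 per hour for technicians or medical assistants and about $87 per hour for physicians, with 35% added for benefits. The section adds: "Direct personnel costs are calculated based on the mean duration for each step".

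Two formulas follow. The person doing the step is costed as mean minutes times (wage rate + benefits). For anyone who assists, "then it will be assumed that they were there for half the time", and the formula is half the mean minutes times the medical-assistant wage plus benefits. No reason is given for the half share or for the single wage. Wages are quoted per hour and time in minutes; neither formula divides by 60 or states the unit of the wage rate.

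Section E.3.d plans univariate and probabilistic sensitivity analyses but does not name staff time or the half-time share among the variables to be changed. Section C.2.c reports the preliminary project's costs: 5 to 14 minutes per step, human costs of $42.44 per participant, non-human costs of $87.34, and $131 per examined patient.

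**The concern.** One section plans measured time and job-specific wages, then appears to set both aside for everyone after the first person at a step. An assumption stands where an observation seems to be available.

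Additional staff are plausible here. Section C.5.c sends a three-person team to Visit 1 (one ocular technician and two study coordinators), and C.6 has a technician and a glaucoma specialist at Visit 2. The plan states no wage for coordinators.

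Step costs feed the cost per diagnosis (a secondary measure in E.3.c), the check of how far reimbursement covers costs (E.3.a), and the net cost of replication in other communities (E.3). Aim 4 distributes protocols and tools, so outside users may apply the formulas as printed.

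**Working it through.** **Inputs** (E.3.a): wages of $16 and $87 per hour, benefits 35%. (C.2.c): steps of 5 to 14 minutes, $42.44 human cost, $131 per patient. Presence of additional staff is not given, so 25% to 100% of the step is assumed as a range.

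**Loaded rates**
- Assistant or technician: 16 x 1.35 = $21.60 per hour; / 60 = $0.36 per minute.
- Physician: 87 x 1.35 = $117.45 per hour; / 60 = $1.9575 per minute.

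**The plan's nearest own figure.** The plan gives no step cost for this trial, so $42.44 can only be checked against a range. Assume that this trial's wages and five steps apply to the preliminary project, with one physician step, four technician steps and no additional staff.
- All steps 5 minutes: 5 x 1.9575 + 4 x 5 x 0.36 = 9.79 + 7.20 = about $17.
- All steps 14 minutes: 14 x 1.9575 + 4 x 14 x 0.36 = 27.41 + 20.16 = about $48.
- C.2.c says the visual field test and physician exam took longest. With those two at 14 minutes and the other three at 5: 27.41 + 5.04 + 5.40 = about $38. The range is then about $38 to $48.
- Minutes multiplied by the hourly rate, without conversion, would give 60 times as much: $1,019.25 to $2,853.90 for the first range.

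The reported $42.44 lies in the converted range and far from the other.

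**Half-time rule, 10-minute step led by a technician, one additional person at assistant pay.** The rule charges that person 5 x 0.36 = $1.80, so the step total is 3.60 + 1.80 = $5.40.

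| Actual presence | Actual cost of additional person | Rule / actual | Actual step total | Rule / actual |
|---|---|---|---|---|
| 25% | $0.90 | 2.0 | $4.50 | 1.20 |
| 50% | $1.80 | 1.0 | $5.40 | 1.00 |
| 75% | $2.70 | 0.67 | $6.30 | 0.86 |
| 100% | $3.60 | 0.5 | $7.20 | 0.75 |

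**Visit 1 team of three, same step, all at assistant pay** (an assumption for the coordinators). The rule gives 3.60 + 2 x 1.80 = $7.20.
- Both helpers present throughout: actual 3 x 3.60 = $10.80, so the rule is one third too low.
- Both present for 25%: actual 3.60 + 2 x 0.90 = $5.40, so the rule is one third too high.

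**Scale per exam, one extra assistant at all five steps of 5 to 14 minutes**
- Present throughout: shortfall of 0.5 x 0.36 x 5 = $0.90 to 0.5 x 0.36 x 14 = $2.52 per step, or $4.50 to $12.60 per exam. Against $131 that is 3.4% to 9.6%.
- Present for 25%: excess of 0.25 x 0.36 x 5 = $0.45 to 0.25 x 0.36 x 14 = $1.26 per step, or $2.25 to $6.30 per exam, which is 1.7% to 4.8%.

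**Would the planned sensitivity analysis cover this?** If the half share were entered without an observed SD, the probabilistic analysis (under E.3.d) would use 10% of the mean, 0.05. That gives 0.5 +/- 1.96 x 0.05, about 40% to 60% of the step, against a possible 0% to 100%.

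**The case against.** The strongest reply is that the half-time rule is a declared simplification, exact when helpers are present for half the step at assistant pay. That stands: the plan contains no presence data, so it is not shown that costs come out too low, or too high.

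It can also be argued that observers time only the person completing the step and that helpers are costed by assumption because nobody times them. The wording allows this, and the reliance on mean step duration is compatible with it. So the text does not prove that recorded times would be thrown away. It does show a gap between recording each staff member's time and assuming the time of some of them, and the plan should close it.

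Materiality is modest. Non-human costs dominated the preliminary project, and the study examinations at Visits 1 and 2 come before or at randomization, so their costs largely cancel in the ICER.

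Three stronger readings are tempting and not supported:
- **A 60-fold costing error.** A reader might infer this from minutes multiplied by hourly wages. A per-minute wage makes the formula correct, and $42.44 fits only a converted calculation. It is a notation slip.
- **A large understatement because a physician helper is priced as an assistant.** No section describes a physician as the additional person for a full step. The Visit 1 team has none, and C.2.c treats the physician exam as a step of its own.
- **A distorted ICER.** The costs concerned are largely shared by the two arms.

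**Conclusion.** The point holds as a limited one. E.3.a plans to record each staff member's time and to use job-specific wages, yet costs additional staff by an unexplained half-time, assistant-pay rule. At assistant pay the charge for that person runs from 2 times actual cost (25% presence) to half of it (100% presence). For a technician-led step with one helper, the step total runs from 1.20 to 0.75 times actual. These figures rest on the plan's wages and an assumed presence range; true direction and size are unknown until presence is observed. Cost per diagnosis, the reimbursement comparison and the replication cost are exposed; the ICER is little affected. The missing division by 60 needs clarifying but is not a demonstrated costing error.

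**What to change.** Replace the two formulas in E.3.a with one: cost of a step = sum, over all staff present, of (recorded minutes / 60) x that person's own hourly wage x 1.35. This uses the planned observations and settles the units. Add a wage for study coordinators from the same labour statistics.

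State whether the observation form times helpers as well as the lead person. Keep the half-time assumption only where a helper's time was not recorded, and vary it from zero to full time when reporting cost per diagnosis and replication cost. Varying it for the ICER alone would show little.

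The cost is rewriting two formulas. If the current form times only the lead person, observers must also log helpers' times during site visits that are already planned.

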During the final closeout visit at the primary care office, patients will be contacted by letter (and follow-up phone call if needed) by a member of the study team and will be scheduled to return to their primary care provider for the following:

- Review of current eye medications
- Review of current systemic medications
- Review of demographics (address & phone number(s))
- Results of A1C reading (from PCP office)
- Blood pressure reading
- Intraocular Pressure reading
- Smoking status
- Completion of Satisfaction Closeout Survey
- Completion of NEIVFQ questionnaire

C.4.b. Specific Roles of Collaboration/Partnerships: The successful implementation of this research project builds upon Wills' current community partnerships from our CDC demonstration project and new collaborations and infrastructure established by the WETD. Our partnerships maximize the capacity of the intervention to reach and identify people with undiagnosed glaucoma, glaucoma suspect, other eye diseases; and visual impairment among high-risk, vulnerable patients they serve. Patients within each organization are racially and ethnically diverse, as described in Facilities. To ensure the broadest reach and ownership of the proposed intervention, our community partners have been invited to collaborate by joining the Advisory Board and engaging in planning, developing, implementing and evaluating the interventions. These partners include the Public Health Management Corporation, Philadelphia Department of Public Health, Health Federation of Philadelphia, and Temple Physicians, Inc. Since each organization has its own detection and referral system for vision and eye care services, we have developed our specific aims and study design with input from our partners and Advisory Board members (Appendix D).

Partners will also assist in remediating organizational, community, and cultural barriers and will provide facilitators and resources to ensure replication of our protocols, results, and outcomes. We believe that the breadth of the governmental, community, non-profit, and university-based partner organizations and the

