The glaucoma specialist will review the results and final diagnosis with each patient. Criteria for glaucoma or glaucoma suspect will be defined as IOP (>21mm Hg), suspicious disks including a cup-to-disk (C:D) ratio greater than 0.5, C:D asymmetry (> 0.2), disk hemorrhage, or a combination of IOP and C:D appearance. Other eye disease diagnoses, such as DR, will be made using standard *AAO Practice Pattern Guidelines*. Assessment measures and study schedule for Visits 1 through 8 are shown in Table 5.

**Table 5: Assessment Measures and Study Schedule** (PCP=Primary care physician, OPHTHO=general ophthalmologist)

Assessment Measures	Eye Detection Exam Visit 1 PCP	Confirm Diagnosis Baseline Visit 2 PCP	Initial Follow-Up Eye Exam Visit 3 OPHTHO	Ongoing Follow-Up Eye Exam Visit 4 OPHTHO	Ongoing Follow-Up Eye Exam Visit 5 OPHTHO	Ongoing Follow-Up Eye Exam Visit 6 OPHTHO	Ongoing Follow-Up Eye Exam Visit 7 OPHTHO	Final Follow-Up Visit 8 or Final Visit PCP & OPHTHO
Medical, family history	✓	✓	✓	✓	✓	✓	✓	✓
Eye fundus photographs	✓							
Complete eye exam		✓	✓	✓	✓	✓	✓	✓

Intraocular pressure**	✓	✓	✓	✓	✓	✓	✓	✓
Central Corneal Thickness*		✓	✓	✓	✓	✓	✓	✓
Visual field test*		✓	✓	✓	✓	✓	✓	✓
Visual acuity (Snellen)*****	✓	✓	✓	✓	✓	✓	✓	✓
Blood pressure (PCP) ***	✓							✓
Hemoglobin A1C (PCP) ***	✓							✓
Body mass index (PCP) ***	✓							✓
Smoking status	✓	✓	✓	✓	✓	✓	✓	✓
NEI-VFQ-25		✓			✓			✓
Satisfaction survey****	✓	✓	✓	✓	✓	✓	✓	✓
Current eye medications								✓
Current systemic meds.								✓
Confirm type of health insurance								✓
Current demographics (address & phone number(s))								✓

\* Testing will be performed at the discretion and according to the follow-up recommendation of the local ophthalmologist

\*\* IOP at Visit 1 & final visit will be measured by iCARE rebound tonometer by study team.

\*\*\* A1C will be captured from the medical record. Blood pressure will be taken at the final visit by a member of the study team.

\*\*\*\* Satisfaction surveys will be administered for Visit 1 and Visit 2 and then 2-4 times a year based on randomization; a study closeout satisfaction survey will be administered at the final visit.

\*\*\*\*\* Visual Acuity (Snellen) will be taken by study team at the final visit.

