**D.1.b. Effectiveness/Efficacy:** We will evaluate the impact of our enhanced intervention on our proposed outcomes, including quality-of-life, and economic efficiency. Determining the effectiveness of our intervention is critically important because patients with undetected glaucoma and other eye diseases can suffer lasting visual impairment that can affect their quality-of-life, economic status, morbidity, and ultimately mortality. New strategies are necessary to improve patient access and utilization of eye care. Our study aims to determine if adherence to follow-up recommendations changes as a result of the enhanced intervention. We will determine the effectiveness of the intervention by examining the effect size associated with our intervention and specified outcomes (adherence to follow-up recommendations and vision-related quality-of-life).

**D.1.c. Adoption:** Our letters of support from Advisory Board members and partner institutions demonstrate a strong commitment and willingness to participate in this research study. We are working closely with primary care offices, health centers, universities, governmental agencies, and community organizations. We expect to notice variations in patient behavior based on the number of resources available to them. These varying settings and intervention modalities are critical to the current and potential impact of our intervention. If differences exist among sites, this is evidence of differential adoption.

**D.1.d. Implementation:** At each setting, implementation refers to the intervention agents' fidelity to all elements of the protocol. This includes consistency of delivery as intended and the time and cost of the intervention. Investigators in coordination with Westat and the project manager will determine the extent to which the intervention was delivered. We will assess implementation by reporting on the percentage of process objectives that were achieved, such as: What proportion of patients received the confirming diagnosis enrolled in the study? How many patients followed up with the general ophthalmologists at the initial 6-month, 1-year, 2-year, and 3-year visits. We will also conduct a cost analysis and report costs of all levels of the intervention, including recruiting patients, reading images, confirming diagnoses, randomization, and 3-year follow-up (Table 7).

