E.3.b. Effectiveness Measure for Aim 3: In addition to conducting a comprehensive examination of costs, we will systematically examine these costs in the context of the intervention's societal benefits by conducting a formal cost-effectiveness analysis. The cost-effectiveness analysis will employ quality-adjusted life years (QALYs) as the primary measure of societal benefits. We will capture QALY over the course of 2 years using the Health Utilities Index, v.2/3 (HUI-2/3). HUI-2/3 is a utility measurement instrument that consists of 15 items that capture 8 attributes of health-related QoL: vision, hearing, speech, ambulation, dexterity, emotion, cognition, and pain.

The scoring algorithm will be obtained from Health Utilities, Inc. and is based on Canadian health preference weights. Utility scores from this instrument range from 0-1, with a higher score indicating better quality-adjusted life. Previous research has shown that the HUI-3 has consistent validity in people with glaucoma, diabetic retinopathy, and cataracts. QALY will be measured as the amount of utility gained or lost over each year of the program.

E.3.c. Incremental Cost-Effectiveness Ratio: The primary cost-effectiveness measure will be defined as the incremental difference between cost of the enhanced intervention and usual care, divided by the difference in health utility-Incremental Cost Effective Ratio (ICER). The ICER thus will indicate the additional costs to bring about one additional unit of benefit (QALY) from the enhanced intervention compared to usual care. The

reference case, which will be defined as usual care. The ICER obtained will be compared to acceptable thresholds of \$50,000 to \$100,000-QALY. A secondary measure will be cost per diagnosis made.

E.3.d. Sensitivity Analysis for Aim 3: To account for uncertainty in our primary ICER, cost and effectiveness data will be entered into a decision analytic model. This is particularly important since the study will be powered based on the primary outcome, not the cost-effectiveness measure. Sensitivity analyses will ensure robustness of the ICER. Both univariate sensitivity analysis (whereby 1 variable is changed at a time and impact on the ICER will be examined), and probabilistic sensitivity analysis (PSA), whereby all relevant variables are simultaneously modified within reasonable ranges will be conducted. Sensitivity analyses will include those variables where we anticipate “real world” uncertainty.

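### HUI-2/3, the source of Aim 3's QALYs, is scheduled at no visit, and section E.3 does not fix one time horizon for QALYs and costs

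*Combined protocol and SAP*

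**What the plan says.** Section E.3.b sets the benefit measure for Aim 3: "The cost-effectiveness analysis will employ quality-adjusted life years (QALYs) as the primary measure of societal benefits". It names the instrument and a window: "We will capture QALY over the course of 2 years using the Health Utilities Index, v.2/3 (HUI-2/3". The next paragraph of E.3.b defines the quantity without that window: "QALY will be measured as the amount of utility gained or lost over each year of the program".

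Section E.3.c defines the numerator: "The primary cost-effectiveness measure will be defined as the incremental difference between cost of the enhanced intervention and usual care". It compares the ICER with thresholds of $50,000 to $100,000 per QALY. Section E.3.a lists what is costed: "Cost measures will include intervention costs, glaucoma-related healthcare service use, glaucoma-related medications, and patient travel costs". Neither section gives a period for these costs. The end of E.3.d says only that the horizon exceeds one year and that costs and benefits are discounted at 3% for each year beyond the first.

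Elsewhere, C.4.a puts follow-up at 6 months and 3 years. D.1.d says that costs will be reported for all levels of the intervention, "including recruiting patients, reading images, confirming diagnoses, randomization, and 3-year follow-up".

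The visit schedule is "Table 5: Assessment Measures and Study Schedule". Its questionnaires are the NEI-VFQ-25 (Visits 2, 5 and 8) and the satisfaction survey. The closeout list in C.4.a has the satisfaction closeout survey and "Completion of NEIVFQ questionnaire". Neither mentions HUI-2/3.

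**The concern.** A QALY difference needs utilities measured in both arms from baseline onward. The analysis plan commits to an instrument that the operational schedule never asks anyone to administer. Staff who follow Table 5 and the closeout list would collect vision-specific quality of life and satisfaction, but no utilities. The plan describes no mapping from NEI-VFQ-25 to utilities that could fill the gap. A baseline utility cannot be collected once a patient has entered follow-up, so finding the omission late would not repair it. Hypothesis 3 would then have no planned data behind it.

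The second issue is that the text allows costs and QALYs to be counted over different periods. An analyst could divide three years of incremental cost by two years of incremental QALYs and still comply with the document. Because the result is judged against fixed thresholds, this choice should be settled before any data are seen.

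**Working it through.** **1. Where HUI-2/3 appears**

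| Place | Quality-of-life or utility item | HUI-2/3? |
|---|---|---|
| E.3.b | HUI-2/3, 15 items | Named, with no visit or date |
| Table 5 | NEI-VFQ-25 (Visits 2, 5, 8); satisfaction survey | No |
| Closeout list, C.4.a | NEI-VFQ; satisfaction closeout survey | No |
| C.6.a and C.6.b | NEI-VFQ-25; satisfaction survey | No |
| Table 7 | Quality of life at Visits 2 and 8, source NEI-VFQ | No |
| Table 8 | Process counts only | No |

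Table 5 goes down to smoking status, insurance type and address, with footnotes on who measures what, so brevity does not readily explain the omission.

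**2. What is said about horizon**

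- QALYs: two years, and also each year of the program (both E.3.b).
- Follow-up: three years (C.4.a).
- Cost reporting: through three-year follow-up (D.1.d, in the RE-AIM evaluation section).
- Costs entering the ICER: no period stated (E.3.a, E.3.c).

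**3. Effect of mixing horizons**

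The plan states no ICER, incremental cost or incremental QALY, so there is no figure to reproduce. The yearly profiles below are assumptions.

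The discount weights at 3% are 1, 1/1.03 = 0.9709 and 1/1.03² = 0.9426.

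- Two-year sum: 1 + 0.9709 = 1.971
- Three-year sum: 1.971 + 0.9426 = 2.913

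Let C₂ and C₃ be discounted incremental costs over two and three years, and Q₂ and Q₃ the same for QALYs. The mixed ICER is C₃/Q₂. Then:

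- mixed ICER ÷ three-year ICER = (C₃/Q₂) ÷ (C₃/Q₃) = Q₃/Q₂
- mixed ICER ÷ two-year ICER = (C₃/Q₂) ÷ (C₂/Q₂) = C₃/C₂

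The first ratio depends only on the QALY profile and the second only on the cost profile. With equal yearly increments, both are 2.913/1.971 = 1.478 (1.50 undiscounted).

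| Assumed yearly increments | vs three-year ICER | vs two-year ICER |
|---|---|---|
| Equal cost, equal QALY | 1.478 | 1.478 |
| All cost in year 1, equal QALY | 1.478 | 1.000 |
| Equal cost, no QALY gain in year 3 | 1.000 | 1.478 |
| Equal cost, QALY gain 1, 0.5, 0.25 | 1.159 | 1.478 |
| Equal cost, QALY gain 1/3, 2/3, 1 | 1.961 | 1.478 |
| Equal cost, QALY 1, 1, −0.5 | 0.761 | 1.478 |
| Cost 1, 1, −0.5, equal QALY | 1.478 | 0.761 |

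For example, the rising profile gives Q₂ = 0.3333 + 0.6667 × 0.9709 = 0.9806 and Q₃ = 0.9806 + 0.9426 = 1.9232, a ratio of 1.961.

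On the plan's own scale, in the equal-increment case:

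- $50,000 × 1.478 ≈ $73,900
- $70,000 × 1.478 ≈ $103,500
- a common-horizon ICER of $100,000/1.478 ≈ $67,700 would appear as $100,000

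**The case against.** Table 5 is not a complete list of economic data. Section E.3.a has staff ask about transport at check-out, and transport has no Table 5 row either. The timeline appendix (Appendix K) and the figures were not in the text I read. A missing row therefore shows that the timing is unspecified, not that HUI-2/3 will never be given. That stands, and it limits the claim to what the schedule as written would produce. The comparison is incomplete, though: E.3.a says when transport is asked, whereas nothing says when HUI-2/3 is given.

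On the horizon, a reader might infer that the plan specifies three-year costs over two-year QALYs, and that the ICER must be either uncomputable or overstated. The documents do not support this. The three-year cost wording is in D.1.d, which is about program cost reporting. Some of what it covers, such as recruitment and image reading, is common to both arms and would largely cancel from an incremental cost. E.3 itself sets no period, and its reference to each year of the program can be read as three-year QALYs. If both quantities run three years, or both stop at two, there is no mismatch. Even with a mismatch, the table shows that the ICER can be overstated, unchanged or understated.

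Aim 3 is also not the primary outcome, and E.3.d acknowledges that the study is not powered on cost-effectiveness. This limits the severity. It does not remove the need for a data source for one of four stated aims.

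**Conclusion.** Two defects stand. First, the only named source of Aim 3's QALYs has no administration time point in any schedule in the text, so the scheduled data cannot yield the ICER. This is more than missing detail, because the schedule and the analysis plan disagree about what is collected.

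Second, E.3.b conflicts internally on the QALY window and E.3 leaves the cost window open. This is an unresolved ambiguity that permits a mismatched ratio; it is not a stated three-year over two-year ratio.

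If the mismatch occurred, the inflation would be about 48% under constant positive yearly increments with 3% discounting. The other assumed profiles give 0.76 to 1.96 times the three-year ICER and 0.76 to 1.48 times the two-year ICER. Overstatement is the likely direction if the intervention costs more and helps in every year, but the documents give no increments from which to confirm that. The change should be made; it does not touch the primary adherence result.

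**What to change.** - **Schedule the instrument.** Add HUI-2/3 to Table 5 and the closeout list for both arms. Take the baseline at Visit 2, or at Visit 1 for patients with elevated pressure who skip Visit 2 and already complete the NEI-VFQ-25 at Visit 1 (note in C.5.c).
- **Use calendar times.** Collect it at fixed annual dates through the chosen horizon and record each date. Copying the NEI-VFQ-25 visits would not do this. At the Table 6 intervals of 1–2 to 12 months, two equal intervals put Visit 5 anywhere from 2 × 1 = 2 to 2 × 12 = 24 months after Visit 3.
- **Match the mode between arms at each time point.** For satisfaction surveys at Visits 3, 4, 6 and 7, C.6.b mails usual care patients and telephones intervention patients. C.6.a puts the Visit 8 NEI-VFQ-25 on the telephone, while C.4.a lists it for the closeout visit at the primary care office. HUI-2/3 should not inherit either difference.
- **State one horizon in E.3** for incremental costs and QALYs: three years, to match follow-up, or both cut at two years. Bring the two E.3.b statements into line with it, and say in D.1.d whether its cost reporting is separate from the ICER.

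The cost is a 15-item questionnaire, largely at existing contacts, with some extra calls where an annual date falls between visits, plus edits to Table 5, the closeout list and E.3.
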